2.4.4.3 Multiplicity issues

Multiplicity will be controlled for the primary analysis (ie, Day 29). Final analysis (ie, Day 60) will be supportive.

For the primary and key secondary endpoints, multiplicity will be controlled via a hierarchical testing procedure in the following order:

1. Primary endpoint sarilumab 400 mg versus placebo
2. Key secondary endpoint sarilumab 400 mg versus placebo
3. Primary endpoint sarilumab 200 mg versus placebo
4. Key secondary endpoint sarilumab 200 mg versus placebo

If one sarilumab dose is discontinued for safety reasons, then all comparisons versus placebo for that dose will be removed and the remaining comparisons will be tested in the order specified above.

2.4.5 Analyses of safety data

The summary of safety results will be presented by treatment group.

General common rules

All safety analyses will be performed on the safety population as defined in [Section 2.3.2](#), unless otherwise specified, using the following common rules:

- The baseline value is defined as the last available value prior to the first dose of study medication.
- The potentially clinically significant abnormality (PCSA) values are defined as abnormal values considered medically important by the Sponsor according to predefined criteria/thresholds based on literature review and defined by the Sponsor for clinical laboratory tests, vital signs, and ECG (see [Appendix A](#))
- PCSA criteria will determine which patients had at least 1 PCSA during the treatment-emergent adverse event period, taking into account all evaluations performed during the treatment-emergent adverse event period, including nonscheduled or repeated evaluations. The number of all such patients will be the numerator for the on-treatment PCSA percentage.
- The treatment-emergent PCSA denominator by group for a given parameter will be based on the number of patients assessed for that given parameter in the treatment-emergent adverse event period by treatment group on the safety population.
- For quantitative safety parameters based on central laboratory/reading measurements, descriptive statistics will be used to summarize results and change from baseline values by visit and treatment group. Summaries will include the endpoint value. The endpoint value is commonly defined as the value collected at the same day/time of the last dose of investigational product. If this value is missing, this endpoint value will be the closest one prior to the last dose intake.
- Selected safety analyses will be summarized by age group, gender, racial subgroups, and any pertinent subgroups as appropriate (eg, number of doses administered).

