PK/Biomarkers (Central Laboratories):											
Serum for PK/Sarilumab Concentration 		X 	X 	X 	X	X	X	X 			X 
ADA		X				X 		X			X
Serum IL-6 		X		X	X	X	X	X			X
Serum sIL-6R 		X 						X			X
Blood for PCR SARS-CoV-2  (Not for determining the inclusion criteria)		X		X	X	X	X	X			X
Pharmacogenomics (optional genomic study):											
Blood for DNA/RNA 		X									

ESO: end of study, SpO2: oxygen saturation, CT-scan: computed tomography ECG: electrocardiogram, WOCBP: women of childbearing potential, PK: pharmacokinetic, ADA: antidrug antibodies, sIL-6R: soluble interleukin 6 receptor, IL: interleukin, PCR: polymerase chain reaction, SARS-CoV-2: Severe acute respiratory syndrome coronavirus 2, DNA: deoxyribonucleic acid, RNA: ribonucleic acid, SAE: serious adverse event, AESI: adverse event of special interest.

1. Laboratory-confirmed SARS-CoV-2 infection (eg by PCR), or other commercial or public health assay in any specimen within 2 weeks prior to randomization and no alternative explanation for current clinical condition is required for inclusion.
2. Screening and baseline may occur within 24 hours. Assessments that are noted for both visits should only be assessed once if the baseline visit is within 24 hours of the screening visit. All baseline samples, if obtained, should be collected before study drug administration at baseline visit except post-infusion PK and sIL-6R samples.
3. Patients will have an end of study (EOS) assessment to collect data on survival, adverse events, and history of hospital re-admission. This assessment may be performed by phone. This visit may be performed earlier if a patient withdraws from the study.
4. Patients discharged prior to Day 29 will have a follow-up phone call on Day 29 to collect data on all adverse events, and history of hospital re-admission.
5. Patients discharged prior to Day 29 should have a sample collected on or before day of discharge. Any sample collected within 24 hours of the day of discharge do not need to be repeated.

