6. Patients may receive a second dose with study drug 24 to 48 hours after the first dose, if the patient meets prespecified criteria in [Section 4.1](#). Day 2 or 3 samples are only taken from patients who are administered a second dose of study treatment. They should be drawn prior to administration of the second dose of study drug to aid in benefit/risk assessment.
7. Sites are required to capture the history of chronic hypercapnic respiratory failure.
8. Body temperature is described in [Section 8.1.2](#) (up to 4 times a day at screening). Retrospective temperature within the previous 24 hours can be considered for screening. Body temperature to be reported in the CRF should be the maximum value observed during any time period or window ([Section 8.1.2](#)).
9. Oxygen delivery and oxygenation: refer to [Section 8.1.2](#) of the protocol for details (up to 4 times a day at screening). Retrospective readings within the previous 24 hours can be considered for screening.
10. Must be measured after 5 minutes of rest (sitting or supine), and must be measured simultaneously with oxygen delivery and ventilation data.
11. Clinical Data Assessments (including 7-point ordinal scale, status of intubation, Intensive care unit admission/discharge, CT scan, X-rays, and any other imaging performed during hospitalization, daily consciousness for NEWS2 scoring system [2]): refer to [Section 8.1.1](#) of the protocol for details.
12. Results as reported to be recorded in arterial blood gas results electronic case report form (CRF) (as available).
13. Vital signs include height (screening only), weight (screening only), blood pressure, pulse, and respiration rate, See [Section 8.2.1](#)
14. The ECG is optional. Historical ECG from current hospital admission is acceptable.
15. Concomitant therapy: refer to [Section 6.5](#) of the protocol for details.
16. Adverse events: All AEs will be recorded in CRF. Note: any abnormal physical findings requiring medical or surgical intervention must be recorded as an AE.
17. Pregnancy testing to be performed locally in women of childbearing potential (WOCBP) only. Serum or urine pregnancy test are both acceptable.
18. Hematology: refer to [Table 11](#) for details.
19. Blood Chemistry: refer to [Table 11](#) for details.
20. Urinalysis is performed at screening (if feasible) and should be collected one additional time (optional) during the treatment period.
21. SARS-CoV-2 detection will be performed locally. This test is optional.

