2.4.3 Extent of investigational medicinal product exposure and compliance

2.4.3.1 Extent of investigational medicinal product exposure

Patients will receive a single dose of study drug on Day 1. Patients may receive a second dose with study drug (based on the original treatment group assigned) 24 to 48 hours after the first dose, if they meet prespecified criteria.

Duration of IMP exposure will be analyzed by summarizing the number of doses patient received by treatment group in the safety population.

A listing will be provided for all study drug administered including the following information:

- Infusion rate (units: mL/h)
- Side and location of drug administration
- Start and end time
- Duration of intravenous infusion
- total dose injected (yes/no)
 - If no and not related to any AE, reason for not administration of total planned dose (Device problem, patient decision, other)
- Evidence of infusion reaction
- infusion interruptions
 - If yes, whether re-administered (yes/no)

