2.4.5.3 Analyses of laboratory variables

Hematology, blood chemistry and urinalysis are performed in local laboratories in this study.

The summary statistics (including number, mean, median, SD, minimum and maximum) of all laboratory variables (laboratory values and changes from baseline) will be calculated for each visit or study assessment (baseline, each post baseline time point, endpoint) by treatment group. This section will be organized by biological function as specified in [Section 2.1.4.3](#).

The incidence of PCSAs (list provided in [Appendix A](#)) at any time during the treatment-emergent adverse event period will be summarized by biological function and treatment group whatever the baseline level and/or according to the following baseline status categories:

- Normal/missing
- Abnormal according to PCSA criterion or criteria

The incidence of abnormal laboratory values at any time during the TEAE period will be summarized in shift tables by biological function and treatment group whatever the baseline level and/or according to the following baseline status categories:

- Normal/Missing
- Abnormal high according to the normal range
- Abnormal low according to the normal range

For parameters for which no PCSA criteria are defined, similar table(s) using the normal range will be provided.

For bacterial infection testing, results will be summarized as number of patients (counts and percent) with negative and positive levels by treatment group.

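### The laboratory 'endpoint' row is tied to the last dose, so on scheduled draws it repeats baseline for one-dose patients and should be deleted or redefined

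*SAP*

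**What the plan says.** The general rules in SAP section 2.4.5 contain both definitions that matter. Baseline: "The baseline value is defined as the last available value prior to the first dose of study medication". Endpoint: "The endpoint value is commonly defined as the value collected at the same day/time of the last dose of investigational product". The fallback for endpoint looks backward only: "If this value is missing, this endpoint value will be the closest one prior to the last dose intake". The bullet holding the endpoint rule opens by limiting itself to quantitative parameters measured centrally.

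SAP section 2.4.5.3 states that hematology, chemistry and urinalysis are done in local laboratories. It requires summary statistics of values and changes from baseline, for all laboratory variables, at "each visit or study assessment (baseline, each post baseline time point, endpoint) by treatment group". Endpoint is thus listed apart from baseline and from the post-baseline visits.

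On dosing, SAP section 2.4.3.1 says: "Patients will receive a single dose of study drug on Day 1". A second dose may follow 24 to 48 hours later if criteria are met.

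On sampling, footnote 2 of the schedule of activities (Protocol section 1.3) says baseline samples "should be collected before study drug administration at baseline visit", apart from post-infusion samples for drug concentration and sIL-6R. Footnote 6 restricts Day 2 or 3 samples to patients who get a second dose, and adds: "They should be drawn prior to administration of the second dose of study drug to aid in benefit/risk assessment". Later hematology and chemistry draws are on Days 4, 7, 15, 21 and 29, or at discharge.

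**The concern.** An endpoint anchored to the last dose suits a trial with repeated dosing over weeks or months, where the last dose falls near the end of observation. Here the last dose is the first dose, or falls one to two days after it, and nearly all laboratory follow-up comes afterwards. The words "commonly defined" are part of the rule itself, and they read like general text that was not adapted to this design.

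At stake is whether one planned row of the laboratory tables carries any information. For one-dose patients it appears to compare a record with itself. For two-dose patients it stops before the second infusion. There is also a gap in scope: if the central-laboratory wording is taken literally, section 2.4.5.3 asks for a row that the SAP does not define.

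**Working it through.** The plan gives no figure for this point, so there is none to reproduce. The check applies the baseline and endpoint rules of SAP section 2.4.5 to the draws in Protocol section 1.3.

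**Step 1: which record each rule selects.** The words on day and time allow two readings: a sample at the time of the last dose, or any sample on that date. Under the second reading, where several samples share a date, the later one is kept (SAP section 2.5.4, rule 2).

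| Pattern | Baseline record | Endpoint record | Change |
|---|---|---|---|
| One dose, screening and Day 1 pre-dose draws | Day 1 pre-dose | the same record | 0 |
| One dose, single combined Day 1 draw | that draw | the same record | 0 |
| One dose, Day 1 draw missing | screening | the same record | 0 |
| One dose, extra unscheduled post-infusion draw on Day 1 | Day 1 pre-dose | same record by time; post-infusion draw by date | 0, or the Day 1 post-infusion change |
| Two doses, Day 2 or 3 sample present | Day 1 pre-dose | Day 2 or 3 sample, before the second dose | change before the second dose |
| Two doses, Day 2 or 3 sample missing | Day 1 pre-dose | the same record | 0 |

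All rows except the fourth give the same result under both readings. In the fourth, SAP Appendix B would still place the extra draw in the Baseline window, because that window takes everything up to Day 1.

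**Step 2: what cannot be selected.** The fallback never moves forward in time, and the second dose is given by Day 3. No scheduled value from Day 4, 7, 15, 21 or 29 can be the endpoint value under either reading.

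**Step 3: what the row would show on scheduled draws.** Let r be the share of patients with a second dose and an available sample before it, and d their mean change at that sample.

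Mean endpoint change = (1 - r) x 0 + r x d = r x d

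Neither r nor d is in the documents. Assuming r between 10% and 30%, 70% to 90% of the endpoint changes come from a record compared with itself. Assuming, for illustration only, a neutrophil change of d = -2.0 x10^9/L:

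- r = 0.10: 0.10 x (-2.0) = -0.2
- r = 0.20: 0.20 x (-2.0) = -0.4
- r = 0.30: 0.30 x (-2.0) = -0.6

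These means would be the same whatever happened to neutrophils from Day 4 onward. The zeros for one-dose patients follow from the rules and do not depend on the assumed values.

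**Step 4: scope.** The defining bullet covers central measurements. Per the schedule of activities, the central assays are drug concentration, anti-drug antibodies, IL-6, sIL-6R and blood SARS-CoV-2 PCR. Their analyses in SAP sections 2.4.5.7, 2.4.6 and 2.4.7 have no endpoint row of this kind, and the vital-signs section (2.4.5.4) lists none. The row is called for only in section 2.4.5.3, for local tests. Either the last-dose rule is carried over to them, with the result above, or the row has no definition.

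**The case against.** The strongest reply is that the rule, read literally, does not govern neutrophils, platelets or ALT, because those tests are local. That is right as a reading of the bullet. It leaves the row in section 2.4.5.3 undefined, so it changes the nature of the defect and not the need for a correction.

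The second reply is that the row is redundant. This stands, and it limits the point considerably:

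- The sentence that asks for the endpoint row also asks for values and changes at each post-baseline time point, and Appendix B lists Days 4 to 29.
- PCSA incidence uses every evaluation in the treatment-emergent period, including unscheduled ones, and the shift tables cover any time in that period.
- SAP section 2.4.7 adds an analysis of neutrophil count by sampling point through Day 29.
- Grade 4 neutropenia and ALT increase are adverse events of special interest with their own summaries.

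A reader might infer that the plan would hide neutrophil lowering or ALT rises and offer false reassurance. The documents do not support that, because a flat endpoint row would sit beside rows showing the post-dose changes.

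A reader might also infer that arm differences in this row would mainly reflect how many patients received a second dose. That is not shown. With arms 1 and 0, the difference is r1 x d1 - r0 x d0. If r is equal in both arms it reduces to r x (d1 - d0), which comes entirely from the early laboratory change.

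Finally, it is too absolute to say that every one-dose patient must have a zero change. An unscheduled post-infusion draw on Day 1 is possible in hospitalized patients and would count under the same-date reading. The exception is narrow.

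**Conclusion.** The point holds in a limited form. The only definition available for the laboratory endpoint row ties it to the last dose. On scheduled draws this gives a change of exactly 0 for one-dose patients and a change taken before the second dose for the rest, with nothing from Day 4 onward. If the central-laboratory wording is taken literally, the row has no definition at all. The SAP needs a correction under either reading.

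The size is minor. One descriptive row is uninformative, and no hypothesis test, error rate, efficacy result or count of adverse events of special interest uses it. The conclusion rests on samples being drawn as the schedule of activities states. The numerical illustration rests on assumed values of r and d and is not needed for the conclusion.

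**What to change.** Preferred: remove endpoint from the list of time points in SAP section 2.4.5.3, and delete the sentences in section 2.4.5 that call for and define the endpoint value. The by-visit and any-time summaries already cover the post-dose period, so nothing is lost.

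If the row is kept, define it for this study as the last available post-dose value within the treatment-emergent period, up to Day 29 or discharge, and state that the definition covers local laboratory data. Add a note that the timing of this value varies with discharge and death: an early discharge may contribute a value near Day 4 and a long stay one near Day 29. Timing may therefore differ between arms, and the row should be read descriptively. Deletion avoids that difficulty.

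Either option is a short wording change to the SAP, best made before the primary database lock. It needs no new data and affects no other planned analysis.

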2.4.5.1 Analyses of adverse events

Generalities

The primary focus of adverse event reporting will be on treatment-emergent adverse events. Pretreatment and posttreatment adverse events will be described separately.

If an adverse event date/time of onset (occurrence, worsening, or becoming serious) is incomplete, an imputation algorithm will be used to classify the adverse event as pretreatment, treatment-emergent, or posttreatment. The algorithm for imputing date/time of onset will be conservative and will classify an adverse event as treatment emergent unless there is definitive information to determine it is pretreatment or posttreatment. Details on classification of adverse events with missing or partial onset dates are provided in [Section 2.5.3](#).

Adverse event incidence tables will be sorted by SOC internationally agreed order and HLGT, HLT, PT by alphabetic order. For adverse event incidence tables presented by SOC and PT, they will be sorted by the internationally agreed SOC order and by decreasing incidence of PTs based

on the Sarilumab 400 mg IV group within each SOC, for the number (n) and percentage (%) of patients experiencing an adverse event. Multiple occurrences of the same event in the same patient will be counted only once in the tables within a treatment phase. The denominator for computation of percentages is the safety population within each treatment group.

Analysis of all treatment-emergent adverse events

The following treatment-emergent adverse event summaries will be generated for the safety population.

- Overview of treatment-emergent adverse events, summarizing total number or number (%) of patients with any
 - Treatment-emergent adverse event
 - Serious treatment-emergent adverse event
 - Severe treatment-emergent adverse event
 - AESI
 - Treatment-emergent adverse event leading to death
 - TEAE leading to study drug interruption or discontinuation
- All treatment-emergent adverse event by primary SOC, HLT, and PT, showing the number (%) of patients with at least 1 treatment-emergent adverse event.
- All treatment-emergent adverse events by primary SOC and PT, showing the number (%) of patients with at least 1 treatment-emergent adverse event.
- All treatment-emergent adverse events by primary SOC, PT and CTC grade, showing the number (%) of patients with at least 1 treatment-emergent adverse event.
- All treatment-emergent adverse events regardless of relationship and related by primary SOC and PT, showing the number (%) of patients with at least 1 treatment-emergent adverse event.
- All treatment-emergent adverse events leading to study drug interruption or discontinuation by Primary SOC and PT, showing the number (%) of patients with at least 1 treatment-emergent adverse event.

Analysis of all treatment emergent serious adverse event(s)

- All treatment-emergent serious adverse events by primary SOC and PT showing the number (%) of patients with at least 1 serious treatment-emergent adverse event.
- All treatment-emergent serious adverse events regardless of relationship and related to IMP, by primary SOC, and PT, showing the number (%) of patients with at least 1 treatment-emergent serious adverse event.

Analysis adverse event of special interest

Unless otherwise specified, AESI will be summarized during the TEAE period by prespecified-grouping (AE category of interest), showing the number (%) of participants, sorted by decreasing

frequency of PT. In addition, summary of TEAE of infusion reactions, ALT increase, and infection events will be provided.

Listings of all adverse events, serious adverse events and AESIs during the study will be provided.

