### **Overall design:**

This study is an adaptive, multi-national, multi-center, phase 3, randomized, double-blind, placebo-controlled trial to evaluate the efficacy and safety of sarilumab in hospitalized adults with severe or critical COVID-19. Patients were randomized in a 2:2:1 ratio to sarilumab 400 mg intravenous (IV), 200 mg IV, or matching placebo IV in a stratified manner prior to Amended Protocol 04. The sarilumab 200 mg IV dose arm will be closed for patients enrolled after Amended Protocol 04 is implemented.

Patients will receive a single dose of study drug on Day 1. Patients may receive a second dose with study drug (based on the original treatment group assigned) 24 to 48 hours after the first dose, if they meet prespecified criteria (see [Section 4.1](#)). Randomization will be stratified by severity of illness (severe OR critical) and use of systemic corticosteroids (Yes OR No).

**Study duration:** An individual patient will complete the study approximately 60 days from screening to follow-up on day  $60 \pm 7$  days. Patients will not be required to return to the hospital once discharged.

**End of study definition:** The end of study (EOS) is defined as the date the last patient completes the last study assessment (in the hospital or via a follow-up phone call if the patient was discharged from the hospital before day 60), withdraws from the study, or is lost to follow-up (ie, the study patient can no longer be contacted by the investigator).

**Population:** Hospitalized adult ( $\geq 18$  years old) male and female patients with COVID-19.

**Disclosure Statement:** This is a parallel group treatment study with 3 arms that is participant and Investigator blinded.

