### **Secondary Endpoints (Safety)**

The safety endpoints are:

- Incidence of serious adverse events
- The incidence of major or opportunistic bacterial or fungal infections
- The incidence of major or opportunistic bacterial or fungal infections in patients with grade 4 neutropenia
- The incidence of hypersensitivity reactions, infusion reactions, gastrointestinal perforation
- White cell count, hemoglobin, platelets, creatinine, total bilirubin, ALT on days 1, 4, 7, 15, 21, 29 (if still hospitalized)

---

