### **9.4.3.2 Safety**

#### **9.4.3.2.1 Adverse events**

Definitions

For safety variables, the following observation period is defined:

The on-treatment period is defined as the day from first dose of study drug to the last dose of study drug plus 60 days.

Treatment-emergent adverse events (TEAEs) are defined as those that are not present at baseline or represent the exacerbation of a pre-existing condition during the on-treatment period.

In addition, there will be an end of study (EOS) phone call follow-up to determine the vital status (alive or dead) of the patient and to assess for SAEs and AESI.

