2.1.4.3 Laboratory safety variables

Clinical laboratory data will include hematology, clinical chemistry, urinalysis and infection tests. Clinical laboratory values will be converted to standard international units; international units will be used in all listings and tables.

Hematology and chemistry data will be collected at screening, baseline, days 2 or 3 (only for patients with second dose), 4, 7, 15, 21 and 29 or discharge. The laboratory parameters will be classified as follows:

- Hematology
 - **Red blood cells and platelets and coagulation:** hemoglobin, hematocrit, platelet count, red blood cell (RBC) count, and RBC indices (MCV, MCH, %Reticulocytes).
 - **White blood cells:** white blood cell (WBC) count and WBC differential (neutrophils, lymphocytes, monocytes, basophils, eosinophils)
- Clinical chemistry
 - **Metabolism:** total proteins, CRP, and glucose (fasting or non-fasting)

- **Electrolytes:** sodium, potassium, and calcium.
- **Renal function:** creatinine, and blood urea nitrogen (BUN).
- **Liver function:** alanine aminotransferase (ALT)/SGPT, aspartate aminotransferase (AST)/SGOT, alkaline phosphatase (ALP), total and direct bilirubin
- Ferritin
- D-dimer

Urine samples will be collected as follows:

- **Urinalysis** - dipstick: pH, blood, glucose, protein, ketones, nitrates, leukocyte esterase, and bilirubin.
- Specific gravity

Infection tests include:

- Bacterial and fungal blood culture

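### Laboratory safety events are tabulated as crude percentages over 60 days although scheduled safety labs stop at discharge or Day 29, so unequal discharge speed distorts the comparison between arms

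*SAP*

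**What the plan says.** **Counting.** The AESIs include Grade 4 neutropenia and ALT increase (SAP 2.1.4.1 and Appendix C). SAP 2.4.5.1 states that "AESI will be summarized during the TEAE period by prespecified-grouping (AE category of interest), showing the number (%) of participants", and for adverse-event tables that "The denominator for computation of percentages is the safety population within each treatment group". Laboratory PCSAs follow a different sentence: under SAP 2.4.5 the denominator "will be based on the number of patients assessed for that given parameter", and "PCSA criteria will determine which patients had at least 1 PCSA during the treatment-emergent adverse event period".

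**Window.** Protocol 9.4.3.2.1: "The on-treatment period is defined as the day from first dose of study drug to the last dose of study drug plus 60 days". SAP 2.1.4 uses the same period for treatment-emergent events.

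**Laboratory schedule.** After baseline, and apart from a Day 2 or 3 draw for patients given a second dose, SAP 2.1.4.3 lists hematology and chemistry at days "4, 7, 15, 21 and 29 or discharge". The protocol's safety endpoints (Table 2) likewise limit laboratory values to patients still in hospital. The overall design adds: "Patients will not be required to return to the hospital once discharged". Contact after discharge is by telephone. Outpatient retesting (Protocol 10.3.2.1) is to be done if possible, and follows up AESIs already found.

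**Adjustment.** The SAP plans no patient-time, time-to-event or competing-risk measure for any safety event. For several efficacy day-counts (SAP 2.4.4.2) it does add a version divided by days of follow-up to death, discharge or last visit.

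**The concern.** A percentage over a common 60-day window compares arms fairly only if events can be detected for a similar time in each. Here the chance of detecting a new laboratory-only event ends, in practice, at the last in-hospital sample. Discharge counts as a primary-endpoint event, so the trial is designed to show that sarilumab brings it forward. If it does, the active arm is tested for less time and its percentages for neutropenia, ALT and PCSAs fall for a reason unrelated to safety. If discharge is slower on sarilumab, the distortion runs the other way. These tables carry the benefit-risk comparison for laboratory effects that the protocol itself anticipates, such as the dose-related fall in neutrophils in Protocol 2.3.

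**Working it through.** **Inputs.** From the documents (Protocol 9.2, SAP 1.3): 45% and 70% with 2-point improvement by Day 15, n about 80 and 160. Assumed, because the documents give no discharge or laboratory event rates: time to improvement is exponential and stands in for discharge; an event is detected if it arises before discharge and missed if it arises later; deaths are ignored.

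**1. The plan's own figure.** Rates are -ln(0.55)/15 = 0.0399 per day (placebo) and -ln(0.30)/15 = 0.0803 per day (sarilumab), ratio 2.01. With follow-up capped at Day 29, expected events are 80 × 0.685 + 160 × 0.902 = 199. Schoenfeld power is then 99.7%, and a two-proportion test at Day 15 has 96.4%. The stated power of at least 90% is reproduced. The plan gives no figure for the safety tables.

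**2. Monitored time to Day 29** = (1 - exp(-29λ))/λ.
- Placebo: 0.685/0.0399 = 17.2 days.
- Sarilumab: 0.902/0.0803 = 11.2 days, ratio 0.65.
- Discharge hazard ratio of only 1.2 (λ = 0.0478): 15.7 days, ratio 0.91.

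At the full effect, 76/55/43/32% of placebo and 57/30/19/10% of sarilumab patients are still in hospital at Days 7/15/21/29. Expected post-baseline draws, including the discharge sample, are 3.6 and 2.8.

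**3. Crude ratio at equal true risk.** If onset is uniform over Days 0 to D, the share arising before discharge is (1 - exp(-λD))/(λD).

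| Onset window | Placebo | Sarilumab | Ratio, full proxy | Ratio, discharge HR 1.2 |
|---|---|---|---|---|
| Days 0-4 | 0.924 | 0.855 | 0.93 | 0.98 |
| Days 0-7 | 0.873 | 0.765 | 0.88 | 0.97 |
| Days 0-15 | 0.753 | 0.581 | 0.77 | 0.95 |
| Days 0-29 | 0.593 | 0.388 | 0.65 | 0.91 |

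With no discharge difference the ratio is 1.00 in every row.

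**4. As percentages, least favourable pattern.** With a constant event hazard h, crude incidence = h/(h+λ) × (1 - exp(-29(h+λ))). At an assumed h of 0.5% per day, equal true risk reads as 8.1% (placebo) against 5.4% (sarilumab). A true rate ratio of 1.5 against sarilumab reads as 8.1% against 7.9%.

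**5. Two candidate remedies, at equal true risk.**
- Events per in-hospital patient-day: the ratio is the crude ratio divided by the monitored-time ratio. That is 0.925/0.654 = 1.41 for onset in Days 0-4 and 0.877/0.654 = 1.34 for Days 0-7. At discharge HR 1.2 and Days 0-4 it is 0.985/0.912 = 1.08. The measure is neutral only when the hazard is constant.
- Cumulative incidence with follow-up ending at the last sample: simulated with 10% true risk, onset over Days 0-7 and non-informative discharge, it returns 10.0% in both arms. The crude percentages are 8.7% and 7.7%.

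**The case against.** Several points on the other side stand.

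- **Not everything after discharge is lost.** A sample is due on or before discharge, unscheduled and repeat tests count toward PCSAs, adverse events are collected by telephone at Days 29 and 60, and outpatient retesting of known AESIs is foreseen. A reader might infer that a patient discharged on Day 5 is simply treated as event-free for 60 days. The documents do not support that: what is missed is a new laboratory-only event arising after discharge.
- **Some tables do show the shrinking sample.** SAP 2.4.5.3 summarizes each laboratory variable by visit and arm with n, and SAP 2.4.7 does so for ANC. It would be wrong to say that no safety output reflects monitoring. But these are summaries of values, not threshold incidence, and later visits describe mainly patients still in hospital.
- **The safety objective is framed as incidence through hospitalization** (Protocol Table 1). For that quantity n/N is a natural estimator, and shorter stay is part of it. The SAP tables, however, are defined over last dose plus 60 days, and the objective is a comparison with control.
- **The 0.65 is near the upper end.** Improvement can come without discharge (3 to 5, for example). The protocol also expects rapid ANC suppression, which points to the upper rows of the table. Against that, Protocol 4.3 reports that higher doses prolonged the maximal response, so risk need not end early.
- **The tables are descriptive and imprecise.** No test depends on them, and an IDMC monitors safety. In step 4 the gap of 2.7 points has a standard error of about 3.5.

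**Conclusion.** The point holds as a conditional one. Scheduled laboratory detection ends at discharge or Day 29, while the AESI and PCSA percentages cover a common 60-day window. If one arm is discharged faster, its laboratory-only events are under-counted relative to the other arm.

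The size rests on assumed discharge and onset patterns. At equal true risk the crude ratio is about 0.65 to 0.93 with the upper-end proxy, 0.91 to 0.98 with a discharge hazard ratio of 1.2, and 1.00 with no discharge difference.

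A reader might infer from step 4 that the plan will hide a 50% excess of harm on sarilumab. The documents do not support that: it needs the full assumed effect to act on discharge and a constant 29-day hazard, and they establish neither. Efficacy conclusions are unaffected. The change is worth making because it is cheap and these tables are where anticipated laboratory harms will be judged.

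**What to change.** In SAP 2.4.5.1 and 2.4.5.3, for Grade 4 neutropenia, ALT increase and laboratory PCSAs, keep the crude percentages and add:

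1. Cumulative incidence to Day 29 by arm, with follow-up ending at the last laboratory sample and death as a competing event, read also at Days 4 and 7. Discharge should not itself be a competing event, since that would largely reproduce the crude percentage.
2. Monitored days and number of draws per arm.
3. A statement that discharge may be informative, because patients who stay are likely to be sicker, so the analysis is supportive and not a full correction.

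Do not use events per in-hospital patient-day to compare arms. For early-onset events it overcorrects against the faster-discharge arm (ratio about 1.3 to 1.4 at equal true risk under the same proxy).

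The cost is SAP wording and a few extra descriptive tables from data already collected, plus an explicit assumption about discharge. No change to study conduct is needed.
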